6.2.1.2. Recording of Adverse Events

AEs should be collected and recorded for each subject from the date he/she signs the ICF until the end of their participation in the study, i.e., the subject has discontinued or completed the study. If a subject is withdrawn prior to randomization, AEs occurring in him/her will not be

collected.

All AEs and SAEs will be recorded in source documents and, if applicable, in relevant eCRF pages and SAE forms. The Investigator is responsible for reporting AEs or SAEs using medical terms if possible.

AEs may be volunteered spontaneously by a subject, or discovered by the study staff during physical examinations or by asking an open, non-leading question such as "How have you been feeling since you were last asked?" All AEs and any required remedial action will be recorded. The type of AE, date (and time, if known) of AE onset, date (and time, if known) of AE end, severity and action taken of the AE will be documented together with the Investigator's assessment of the seriousness of the AE and causal relationship to IP and/or study procedure.

All AEs should be recorded using standardized medical terms. AEs will be coded using the Medical Dictionary for Regulatory Activities (MedDRA).

6.2.1.3. *Assessment of Adverse Events*

Each AE will be assessed by the Investigator with regard to the categories discussed in the following sections.

6.2.1.3.1. *Severity*

The Investigator will assess all AEs for severity in accordance with the following standard ratings.

- Mild: Ordinarily transient symptoms, does not influence performance of a subject's daily activities. Treatment is not ordinarily indicated.
- Moderate: Marked symptoms sufficient to make a subject uncomfortable. Moderate influence on performance of a subject's daily activities. Treatment may be necessary.
- Severe: Symptoms cause considerable discomfort. Substantial influence on performance of a subject's daily activities. May be unable to continue in the study and treatment may be necessary.

When changes in the intensity of an AE occur more frequently than once a day, the maximum intensity for the event should be noted for that day. Any change in severity of signs and symptoms over a number of days will be captured by recording a new AE, with the amended severity grade, and the date (and time, if known) of the change.

6.2.1.3.2. *Causality*

The Investigator will assess the causality/relationship between the IP and the AE. One of the categories described in [Table 6](#) should be selected based on medical judgment, considering the definitions below and all contributing factors.

Table 6 Assessment of Relationship of Adverse Events to Investigational Product

Related	
The AE follows a reasonable temporal sequence from IP administration, and cannot be reasonably explained by a subject's clinical state or other factors (e.g., disease under study, concurrent diseases, or concomitant medications).
 
The AE follows a reasonable temporal sequence from IP administration, and

---------	---

	
represents a known reaction to the drug under study or other drugs in its class, or is predicted by the known pharmacological properties of the drug.
 
The AE cannot be judged because of insufficient or contradictory information.
 
The AE cannot be supplemented or verified.

Not related	
The AE does not follow a reasonable temporal sequence from IP administration, or can be reasonably explained by a subject's clinical state or other factors (e.g., disease under study, concurrent diseases, and concomitant medications).

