4.4. Subject Withdrawal and Replacement

Subjects may withdraw consent to participation in the clinical study at any time without penalty and for any reason without prejudice to his or her future medical care. The subject does not need to give a reason for withdrawal of consent to participation in the clinical study. Subject participation may be terminated prior to completing the study and the reason recorded as follows:

- Adverse event
- Protocol violation
- Loss to follow-up
- Subject withdraws consent.
- Study discontinuation by the Sponsor
- Withdrawn by the Principal Investigator
- Pregnancy
- Other

In all cases, the reason(s) for withdrawal must be recorded. Should the randomization code be broken for a subject, the date, time and reason must be recorded.

If a subject is withdrawn, or chooses to withdraw, from the clinical study for any reason, the Principal Investigator must make every possible effort to perform the evaluations described for the Follow-up visit.

Once a subject who was administered IP is withdrawn by the Principal Investigator, the subject may not re-enter the study.

A subject who has been withdrawn from the study before IP administration may be replaced with a candidate subject. Subjects withdrawn from the study for reasons unrelated to safety may be replaced at the discretion of the Investigator and the Sponsor. The study results obtained until their withdrawal may be reviewed for final evaluation. The numbers given to replaced subjects are described in Section 5.5.2.

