6.2. Safety Variables

6.2.1. Adverse Events

AE reporting will begin for each subject from the date he/she signs the ICF and will continue until the Follow-up visit.

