6.2.1.3.3. Seriousness

Severity is a measure of intensity whereas seriousness is defined by the criteria in Section 6.2.1.1.2.

6.2.1.4. *Reporting of Serious Adverse Events*

All SAEs that occur during the period of observation (from the date the subject signs on the ICF until the follow-up visit), whether they are considered to be related to the IP or not, must be reported to the Sponsor within 24 hours after becoming aware of the occurrence by fax or email via the completed SAE report.

Serious AEs occurring after the Follow-up visit (end of the clinical study) should be reported to the Sponsor by the Principal Investigator if the Principal Investigator considers there is a reasonable causal relationship with the IP.

The minimal information required for an initial report is:

- Sender of report (name, address of Principal Investigator)
- Subject identification (Screening/randomization number, **NOT** subject name)
- Protocol number
- Description of SAE (Start date, seriousness)
- Details of the IP (Dosage, frequency, start date, end date)
- Causality assessment

However, as far as possible all points on the SAE form should be covered in the initial report, and the completed SAE form must be faxed or emailed to the Sponsor.

After receipt of the initial report, the Sponsor will review the information and, if necessary, contact the Principal Investigator to obtain further information for assessment of the event. The Principal Investigator will be responsible for informing the IRB of the SAE, and the Sponsor will be responsible for informing the regulatory authorities of the SAE as per local requirements.

Serious Adverse Event Reporting:

Hanmi Pharmaceutical Co., Ltd. Drug Safety & PV Team

[contact]

[contact]

Email: [contact]

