- Benzodiazepines (BZO)
- Cannabinoids (THC)
- Cocaine (COC)
- Opiates (OPI)
- Phencyclidine (PCP)

Pregnancy Testing

- Serum/urine human beta chorionic gonadotrophin (all females)

The Principal Investigator or the Investigator at the institution will indicate whether or not any value outside the normal range is of clinical significance. If the result of any test (or repeat test, if done) from the samples taken during the Screening period is indicated as clinically significant, the subject's participation in the study will be decided based on the Principal Investigator's medical judgment. Additional testing during the study may be done if medically indicated. If a clinically significant abnormality is found in the samples taken from the date the ICF is signed until the Follow-up visit, it should be recorded as an AE and the subject will be followed until the test(s) has (have) normalized or stabilized, at the discretion of the Principal Investigator.

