7.6. Termination Visit

Subjects who withdraw consent or are withdrawn from the clinical study should, if possible, have a termination visit. This visit should take place as soon as possible after the subject withdrew consent or was withdrawn from the clinical study. For patients who have been dosed with the IP, they will make a termination visit within 30 days after the administration, if possible. The assessments and procedures scheduled for the Follow-up visit should be performed at the termination visit.

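### After a dosed subject leaves early, collection of new adverse events can end before the cohort's planned Follow-up day; one added sentence would close most of that gap.

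*Protocol*

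**What the plan says.** **End of collection.** Protocol 6.2.1.2 (Recording of Adverse Events) has AEs recorded from consent "until the end of their participation in the study, i.e., the subject has discontinued or completed the study". Section 6.2.1 puts the end elsewhere: "AE reporting will begin for each subject from the date he/she signs the ICF and will continue until the Follow-up visit". Section 6.2.1.4 uses the Follow-up visit as the end of the SAE observation period, and 6.2.2 uses it for clinically significant laboratory findings that count as AEs. After that visit, 6.2.1.4 asks for an SAE to be reported "if the Principal Investigator considers there is a reasonable causal relationship with the IP".

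**Subjects who leave early.** Under 4.4, "the Principal Investigator must make every possible effort to perform the evaluations described for the Follow-up visit"; no day is given. Section 7.6 has those assessments done at a termination visit and says of its timing: "This visit should take place as soon as possible after the subject withdrew consent or was withdrawn from the clinical study". It adds: "For patients who have been dosed with the IP, they will make a termination visit within 30 days after the administration, if possible". Note b to Tables 1-1 and 1-2 also covers early leavers. It calls the visit the Follow-up visit and aims for it within 30 days of discontinuation or withdrawal of consent.

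**Planned Follow-up.** This is Day 30 (±3 days) in Cohorts 1-3 and Day 44 (±3 days) in Cohorts 4-5 (Tables 1-1 and 1-2; SAP 2.1). AE assessment is scheduled at both.

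**The concern.** Stopping treatment often ends exposure. Here it cannot, because the whole dose is given on Day 1 and section 1.1 describes a molecule built for a longer half-life. A dosed subject who leaves on Day 8 may still carry drug. Section 7.8.2 anticipates delayed hypersensitivity in the weeks after dosing, and a termination visit on Day 8 to 10 takes place only 7 to 9 days after the dose.

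Safety is the primary objective and each dose level has six active subjects, so one subject is 1/6 = 17% of a dose group. SAP 4.1 keeps every dosed subject in the Safety Set, and SAP 6.2.1 tabulates subjects with events as counts and percentages, with no allowance for time observed. An early leaver with a short AE window therefore enters the denominator as if fully observed.

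**Working it through.** The plan gives no figure of its own on this point. The check is a reading of the sections together, followed by day arithmetic.

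**Can the sections be reconciled?** Yes. If the termination visit is treated as that subject's Follow-up visit, as note b's wording and the transfer of assessments in 7.6 suggest, then 6.2.1, 6.2.1.2, 6.2.1.4 and 6.2.2 can all end on the same day. That settles when collection stops. It does not make it last until Day 30 or Day 44, because neither 7.6 nor note b sets an earliest day for the visit.

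**Inputs.** Dosing is on Day 1. Planned Follow-up F is Day 30 or Day 44. Post-dose days to Follow-up are F − 1, that is 29 or 43. The discontinuation day is set at Day 8 as an example; the documents give no expected timing or number of discontinuations.

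**Possible visit days for a Day 8 discontinuation**
- Immediate visit: Day 8.
- Section 7.6 limit, 30 days from dosing: 1 + 30 = Day 31.
- Note b limit, 30 days from discontinuation: 8 + 30 = Day 38.

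**Uncovered days** = max(0, F − visit day)

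| Termination visit | Cohorts 1-3 (F = 30) | Cohorts 4-5 (F = 44) |
|---|---|---|
| Day 8 | 30 − 8 = 22 (22/29 = 76%) | 44 − 8 = 36 (36/43 = 84%) |
| Day 31 | 0 | 44 − 31 = 13 (13/43 = 30%) |
| Day 38 | 0 | 44 − 38 = 6 (6/43 = 14%) |

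With the ±3-day Follow-up window, Day 44 becomes Day 41 to 47. The 13 days become 10 to 16, and the 6 days become 3 to 9.

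A literal reading of 6.2.1.2, with recording stopping at discontinuation itself, gives the same 22 and 36 days as the immediate visit.

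**Other discontinuation days.** With an immediate visit on Day 10 the uncovered days are 20 and 34; on Day 17 they are 13 and 27. At the note b limit, Cohorts 1-3 are always covered to the nominal Day 30. Cohorts 4-5 are covered to Day 44 only for discontinuation on Day 14 or later (14 + 30 = 44).

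**What is lost in the interval**
- AEs already known are not lost: 6.2.1.5 follows them to resolution or stabilisation, whatever the cause.
- SAEs considered related stay reportable under 6.2.1.4. Table 6 classes an event that cannot be judged or verified as related. If that scale governs the later rule, only SAEs with no plausible timing or with another reasonable explanation fall outside it.
- What remains is new non-serious AEs and SAEs assessed as not related.

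**The case against.** The strongest reply is that there is no real conflict. Once the termination visit stands in for Follow-up, the sections agree, and ending collection of new non-serious AEs at the last visit is a recognisable design. That stands as far as consistency goes. A reader might infer from 6.2.1 and 6.2.1.2 that the protocol flatly contradicts itself, and the documents do not support that. Agreement on an early end is still an early end, however.

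Second, 22 and 36 days are the top of a range. Note b allows a visit as late as Day 38 for a Day 8 leaver, and both limits are best-effort. This also stands, which is why the range is shown. The preference in 7.6 for a prompt visit makes the upper end realistic.

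Third, few subjects would benefit. Those lost to follow-up cannot be reached, those who withdraw consent may decline contact, and those who leave because of an AE have that AE followed. This stands and limits the importance of the point.

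A reader might also infer that subjects are left without care. Section 10.2 provides treatment for AEs during and after the study, so only data collection is affected. Nor do the documents show that the 30 days in 7.6 are left over from the Day 30 schedule; that would be a guess.

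**Conclusion.** The gap is real but small, and worth closing because closing it is cheap. As written, collection of new AEs in a dosed early leaver can end before the cohort's planned Follow-up. For a Day 8 discontinuation, the uncovered interval runs from 0 to 22 days in Cohorts 1-3 and from 6 to 36 days in Cohorts 4-5, depending on when the termination visit takes place.

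These are calendar days. They say nothing about how likely an event is. The result rests on the assumed Day 8 discontinuation and on taking the termination visit as the end of collection. The number of subjects affected cannot be computed, because no dropout rate is given. Without a human half-life, the importance of Days 31 to 44 cannot be judged.

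A reader might go further and infer that the safety results or an escalation decision would be distorted. Some stopping criteria in 3.4 count events in two or more subjects, so a missed event could matter in principle. Nothing in the documents shows that one would.

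**What to change.** In 6.2.1.2, replace the clause introduced by i.e. rather than simply deleting it, since it is the only definition of the end of participation. The new text should say:
- for subjects who complete the study, collection ends at the Follow-up visit;
- for dosed subjects who discontinue and do not refuse contact, AEs and SAEs, with any medication used to treat them, are collected to the cohort's planned Follow-up day (Day 30 in Cohorts 1-3, Day 44 in Cohorts 4-5), by one telephone contact if the termination visit was earlier.

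For subjects who accept the contact, this brings the uncovered interval to zero in both sets of cohorts.

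Separately, 7.6 counts its 30 days from dosing and note b counts from discontinuation. Using one starting date would tidy the wording, but a limit on the visit does not by itself extend collection.

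The cost is one or two sentences of protocol text and at most one call per dosed early leaver. Subjects who withdraw consent may decline the call, so the gap cannot be closed for everyone.

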6.2.1.3.3. Seriousness

Severity is a measure of intensity whereas seriousness is defined by the criteria in Section 6.2.1.1.2.

6.2.1.4. *Reporting of Serious Adverse Events*

All SAEs that occur during the period of observation (from the date the subject signs on the ICF until the follow-up visit), whether they are considered to be related to the IP or not, must be reported to the Sponsor within 24 hours after becoming aware of the occurrence by fax or email via the completed SAE report.

Serious AEs occurring after the Follow-up visit (end of the clinical study) should be reported to the Sponsor by the Principal Investigator if the Principal Investigator considers there is a reasonable causal relationship with the IP.

The minimal information required for an initial report is:

- Sender of report (name, address of Principal Investigator)
- Subject identification (Screening/randomization number, **NOT** subject name)
- Protocol number
- Description of SAE (Start date, seriousness)
- Details of the IP (Dosage, frequency, start date, end date)
- Causality assessment

However, as far as possible all points on the SAE form should be covered in the initial report, and the completed SAE form must be faxed or emailed to the Sponsor.

After receipt of the initial report, the Sponsor will review the information and, if necessary, contact the Principal Investigator to obtain further information for assessment of the event. The Principal Investigator will be responsible for informing the IRB of the SAE, and the Sponsor will be responsible for informing the regulatory authorities of the SAE as per local requirements.

Serious Adverse Event Reporting:

Hanmi Pharmaceutical Co., Ltd. Drug Safety & PV Team

[contact]

[contact]

Email: [contact]

6.2.1.5. Follow-up of Adverse Events

All AEs experienced by a subject, irrespective of the suspected causality, will be monitored until the event has resolved, until any abnormal laboratory values have returned to baseline or stabilized at a level acceptable to the Principal Investigator, until there is a satisfactory explanation for the changes observed or until the subject is lost to follow-up.

If there are any changes of condition in subjects reported with SAEs (e.g., discharge after admission, situation worsened) or if any additional information is collected, the Investigator will complete an SAE report and send it to the Sponsor by fax or email within 24 hours after becoming aware of the occurrence.

6.2.1.6. Suspected Unexpected Serious Adverse Reactions

Any AE that is considered to be a suspected unexpected serious adverse reaction (SUSAR) has additional reporting requirements, as described below:

- If the SAE is fatal or life-threatening, associated with the use of the IP, and unexpected, the Sponsor will report it to the regulatory authorities within 7 calendar days after the Sponsor learns of the event, and the Principal Investigator will report it to the IRB in accordance with the institution regulations. If the required information in the SAE report is not fully reported, however, the Sponsor will report additional follow-up information to the regulatory authorities within 15 calendar days after the Sponsor first learns of the event, and the Principal Investigator will make an additional report in accordance with the institution regulations.
- If the SAE is not fatal or life-threatening but is otherwise serious, associated with the use of the IP, and unexpected, the Sponsor will report it to the regulatory authorities within 15 calendar days after the Sponsor learns of the event, and the Principal Investigator will report to the IRB in accordance with the institution regulations.

The Sponsor will notify the Principal Investigator of relevant information about SUSARs that could adversely affect the safety of subjects in a timely fashion. Follow-up information may be submitted if necessary.

6.2.1.7. *Pregnancy*

The Sponsor has a responsibility to monitor the outcome of all pregnancies reported during the clinical study.

Pregnancy alone is not regarded as an AE unless there is a suspicion that the IP may have interfered with the effectiveness of a contraceptive medication. Elective abortions without complications should not be regarded as AEs, unless they were therapeutic abortions (see below). Hospitalization for normal delivery of a healthy newborn should not be considered an SAE.

If a female subject is confirmed to be pregnant, IP administration will be stopped and her participation in the clinical study will be terminated. Immediately after becoming aware of a subject's pregnancy, the Investigator should report to the Sponsor the fact that she is pregnant together with the subject number and receive her consent that her pregnancy information will be collected and shared with the Sponsor. If the subject agrees, the Investigator must report to the Sponsor via the completed Clinical Trial Pregnancy Report; initial report within 24 hours after obtaining the subject's consent. Any pregnancy of a male subject's partner must also be reported to the Sponsor in the same manner as the pregnancy in a female subject. The Principal Investigator must follow-up and document the course and the outcome of all pregnancies even if the subject has been withdrawn from the clinical study or if the clinical study has finished. All outcomes of pregnancy (e.g., the normal delivery or elective abortion) must be reported by the Principal Investigator to the Sponsor via the completed Clinical Trial Pregnancy Report; follow-up report within 24 hours after becoming aware of the outcome.

Any SAE that occurs during pregnancy must be recorded on the SAE report form (e.g., maternal serious complications, therapeutic abortion, ectopic pregnancy, stillbirth, neonatal death, congenital anomaly, birth defect) and reported within 24 hours (based on the calendar day) in accordance with the procedure for reporting SAEs.

6.2.2. Clinical Laboratory Assessments

The clinical laboratory tests specified in [Table 7](#) will be determined at time points specified in the Schedule of Assessments ([Table 1-1](#) and [1-2](#)).

Clinical laboratory tests will be performed by the laboratories specified in the Laboratory Manual(s). Samples will be collected in appropriate tubes and handled according to standard procedures of the applicable laboratory.

Table 7 Clinical Laboratory Assessments

Hematology	
• White blood cell (WBC) count	• Neutrophils (percentage and absolute count)
• Red blood cell (RBC) count • Lymphocytes (percentage and absolute count)	• Lymphocytes (percentage and absolute count)
• Hemoglobin (Hb)	• Monocytes (percentage and absolute count)
• Hematocrit (HCT)	• Eosinophils (percentage and absolute count)
• Mean corpuscular volume (MCV)	• Basophils (percentage and absolute count)
• Mean corpuscular hemoglobin (MCH)	• Platelet count
• Mean corpuscular hemoglobin concentration (MCHC)	• RBC distribution width (RDW)
Clinical Chemistry	
[Blood glucose-related panel]	
• Fasting plasma glucose (FPG)	
[Lipid-related panel]	
• Total cholesterol	• Triglyceride
• Low-density lipoprotein (LDL)	• Free fatty acid
• High-density lipoprotein (HDL)	
• Very low-density lipoprotein (VLDL)	
[Liver function test]	
• Alanine aminotransferase (ALT)	• Total bilirubin
• Aspartate aminotransferase (AST)	• Direct bilirubin
• Alkaline phosphatase (ALP)	• Total protein
• Lactate dehydrogenase (LDH)	• Albumin
• Gamma glutamyl transferase (GGT)	• Prealbumin
	• Albumin/globulin ratio (A/G ratio)
[Pancreas function test]	
• Amylase	• Lipase
[Kidney function test]	
• Blood urea nitrogen (BUN)	• Creatinine
• Sodium	• Potassium
• Calcium	• Chlorine
• Uric acid	• Phosphorus
• Creatine kinase (CK)	
• hs-CRP	
• Follicle-stimulating hormone (FSH) (Screening visit only; postmenopausal female subjects only)	

Coagulation

- Activated partial thromboplastin time (PTT)
- Prothrombin time (PT) (sec)
- International normalized ratio (INR)

Urinalysis

- Bilirubin
- Glucose
- Ketone
- White blood cell (WBC)
- Nitrite
- Microscopic (WBC, RBC and squamous cell)
- Blood (Occult blood)
- pH and specific gravity (SG)
- Albumin
- Urobilinogen

Viral Serology

- Hepatitis B core antibody (anti-HBc)
- Hepatitis B surface antigen (HBsAg)
- Hepatitis C antibody (HCV Ab)
- Human immunodeficiency virus (HIV) antibody
- Syphilis reagin

Urine Drug Screening

- Amphetamines (AMP)
- Barbiturates (BAR)
- Benzodiazepines (BZO)
- Cannabinoids (THC)
- Cocaine (COC)
- Opiates (OPI)
- Phencyclidine (PCP)

Pregnancy Testing

- Serum/urine human beta chorionic gonadotrophin (all females)

The Principal Investigator or the Investigator at the institution will indicate whether or not any value outside the normal range is of clinical significance. If the result of any test (or repeat test, if done) from the samples taken during the Screening period is indicated as clinically significant, the subject's participation in the study will be decided based on the Principal Investigator's medical judgment. Additional testing during the study may be done if medically indicated. If a clinically significant abnormality is found in the samples taken from the date the ICF is signed until the Follow-up visit, it should be recorded as an AE and the subject will be followed until the test(s) has (have) normalized or stabilized, at the discretion of the Principal Investigator.

